APPENDIX 2. HANIFIN AND RAJKA DIAGNOSTIC CRITERIA FOR ATOPIC DERMATITIS

Hanifin and Rajka Diagnostic Criteria for Atopic Dermatitis (AD)

Major criteria: Must have three or more of:

1. Pruritus
2. Typical morphology and distribution
 - Flexural lichenification or linearity in adults
 - Facial and extensor involvement in infants and children
3. Chronic or chronically-relapsing dermatitis
4. Personal or family history of atopy (asthma, allergic rhinitis, atopic dermatitis)

Minor criteria: Should have three or more of:

1. Xerosis
2. Ichthyosis, palmar hyperlinearity, or keratosis pilaris
3. Immediate (type 1) skin-test reactivity
4. Raised serum IgE
5. Early age of onset
6. Tendency toward cutaneous infections (especially *S aureus* and herpes simplex) or impaired cell-mediated immunity
7. Tendency toward non-specific hand or foot dermatitis
8. Nipple eczema
9. Cheilitis
10. Recurrent conjunctivitis
11. Dennie-Morgan infraorbital fold
12. Keratoconus
13. Anterior subcapsular cataracts
14. Orbital darkening
15. Facial pallor or facial erythema
16. Pityriasis alba
17. Anterior neck folds
18. Itch when sweating
19. Intolerance to wool and lipid solvents
20. Perifollicular accentuation
21. Food intolerance
22. Course influenced by environmental or emotional factors
23. White dermographism or delayed blanch

(Hanifin, 1980)

[figure not shown]

## INTRODUCTION

The purpose of this statistical analysis plan (SAP) is to provide a description of the statistical analyses performed for the Phase 2a protocol, ATI-502-AD-201, V1.0 (23Apr2018).

## 1. STUDY OBJECTIVES

### 1.1 Primary Objective

The primary objective for this study is to assess the safety and tolerability of ATI-502 Topical Solution, 0.46% in subjects with moderate to severe atopic dermatitis.

### 1.2 Secondary Objectives

The secondary outcome measures for this study are to assess the following:

- Change from baseline in Physician Global Assessment (PGA) score following 4 weeks of treatment with ATI-502 Topical Solution, 0.46%
- Change from baseline in body surface area affected by atopic dermatitis following 4 weeks of treatment with ATI-502 Topical Solution, 0.46%.
- Change from baseline in Eczema Area and Severity Index (EASI) score following 4 weeks of treatment with ATI-502 Topical Solution, 0.46%.
- Change from baseline in the subjects Signs of Atopic Dermatitis (SAD) assessment following 4 weeks of treatment with ATI-502 Topical Solution, 0.46%.
- Change from baseline in Subjects Pruritus Assessment (SPA) score following 4 weeks of treatment with ATI-502 Topical Solution, 0.46%...

## 2. STUDY DESIGN

This is an open label, multicenter, phase 2a study designed to evaluate the safety and tolerability of ATI-502 Topical Solution, 0.46% in male and female subjects with a diagnosis of AD as defined by the Hanifin and Rajka criteria. Based on the 5-point Physician's Global Assessment (PGA) scale, subjects must have a score of 3 (moderate) or 4 (severe). Subjects will be required to apply ATI-502 study medication to their identified AD treatment areas twice a day (BID) for a total of 4 weeks. Subjects will be allowed to treat new disease areas with ATI-502 Topical Solution, 0.46% if they appear after Visit 2. All subjects will be required to complete a safety follow up visit 4 weeks post last study medication application.

A total of 30 evaluable subjects who are  $\geq$  18 years of age with a clinical diagnosis of moderate or severe AD will be enrolled to the study.

Safety and tolerability will be evaluated by assessment of adverse events, physical examinations, vital signs, ECGs and clinical laboratory tests.

### **3. SCHEDULE OF ASSESSMENTS**

The study schedule of assessments can be found in Table 1.

**Table 1 Schedule of Assessments**

	Screening	Baseline	Treatment			Post Treatment Safety Follow up Visit 
	Visit 1	Visit 2	Visit 3	Visit 4	Visit 5	Visit 6
Week		0	1	2	4	8
Treatment Day	-14 to 0	1	8	15	29	56
Treatment Window(days)	N/A	N/A	± 3	± 3	± 3	+7
Informed consent 	▲					
Inclusion/exclusion criteria	▲	▲				
Physical exam 	▲					▲
Demographics & Medical History	▲					
Vital Signs 	▲	▲	▲	▲	▲	▲
Fitzpatrick Skin Type	▲					
Atopic Dermatitis History 	▲					
Clinical Chemistry and CBC 	▲	▲	▲	▲	▲	▲
QuantiFERON Gold 	▲					
Virology [HepB (HBsAg), HCV (antibody), HIV (antibody)]	▲ 					
Serum Pregnancy	▲					
Urine Pregnancy		▲				▲
ECG	▲		▲	▲	▲	▲
Physician's Global Assessment (PGA)	▲	▲	▲	▲	▲	▲
Body Surface Areas Assessment	▲	▲	▲	▲	▲	▲
Identification of AD Treatment Area	▲	▲				
Eczema Area and Severity Index (EASI)	▲	▲	▲	▲	▲	▲
Subjects Pruritus Assessment (SPA)		▲	▲	▲	▲	▲
Signs of Atopic Dermatitis (SAD)		▲	▲	▲	▲	▲
Standardized Photography 	▲	▲	▲	▲	▲	▲
Dispensing of study medication 		▲	▲	▲		
Treatment with ATI-502		▲ 	▲	▲	▲	
Subject Instructions 	▲	▲	▲	▲	▲	
Concomitant medications/therapies	▲	▲	▲	▲	▲	▲
Adverse Events 	▲	▲	▲	▲	▲	▲

 A written, signed ICF must be obtained from each subject prior to performing any study related procedure.

 A physical exam includes: general appearance, examination of head, eyes, ears, nose and throat, extremities, respiratory, cardiovascular, abdominal, neurological, musculoskeletal, lymphatic and skin assessment.

 Vital signs include: oral or ear temperature, blood pressure, heart rate, respiration rate (height and weight at baseline only).

 Prior therapies or treatments a subject received to treat AD must be documented for each subject.

 Serum chemistry panel to include: albumin, alkaline phosphatase, ALT, AST, BUN, bicarbonate, calcium, chloride, creatinine, glucose, lactate dehydrogenase (LDH), phosphorus, potassium, sodium, total bilirubin, total protein, uric acid, total cholesterol, LDL, HDL triglycerides, and complete blood count including differential.

 All subjects must have a blood sample drawn to test for the tuberculosis virus (QuantiFERON Gold). The blood sample will be sent to a central laboratory for analysis and results must be received prior to enrolling the subject.

 All subjects will be required to have virology testing for HepB (HBsAG), HCV(antibody), and HIV (antibody). If a subject demonstrates to have serological evidence HepB (HBsAG), HCV (antibody) or HIV (antibody), the subject will not be allowed to enroll to the study.

 Canfield staff will review all photographs within 2 days of the photographs being submitted. If a re-take is required, Canfield will notify the site and the re-take photographs will need to be performed within 7 days of the visit. Prior to enrollment to the study, each subject's Visit 1 photos will be reviewed by a panel of board certified dermatologists to ensure that the subject's target areas for treatment meet the study entry criteria.

 At visit 2, following confirmation that the subject is approved for enrollment to the study, the site will weigh and dispense supplies of ATI-502 study medication and disposable droppers to the subject for at home application of the study medication.

 All subjects will have their first application of study medication applied in the clinic during Visit 2. Subjects will continue to apply ATI-502 Topical Solution, 0.46% to all target areas twice a day for 4 weeks (Day 28) unless the subject meets the criteria for treatment interruption. If new areas of AD develop, subjects will be allowed to treat these areas with the ATI-502 study medication.

 Sites will be required to review with each subject the proper application of the study medication and remind that they must refrain from exercise that may cause excessive sweating, bathing or swimming for a period of 6 hours after the application of study medication. Subjects are also to be reminded that they may not apply moisturizers, emollients, or sunscreen to target AD areas during protocol treatment.

 All non-serious AEs will be collected from the time of first study medication application until the final study visit. Serious AEs will be collected from the time of consent through the final study visit.

 A final safety follow up visit will be conducted at week 8 (Visit 6). For those subjects that discontinue the study early, they must return to the clinic 4 weeks following the last study medication application for a final safety visit.

## **4. STATISTICAL METHODS**

Summaries will be presented for all subjects combined.

All Data listings will be sorted by subject ID, and where applicable date/study day.

### **4.1 Study Population, Disposition, Baseline Characteristics, Medical History Concomitant Medications, Exposure and Protocol Violations**

#### **4.1.1 Analysis Populations**

Safety Population: Includes all subjects with at least one application of study medication. The Safety Population will be used for all safety analyses.

Efficacy Population: Includes all subjects with at least one application of study medication. The Efficacy Population will be used for all efficacy analyses.

Per-Protocol (PP) Population: Includes all subjects who completed Visit 6 (Week 8). The PP Population will be used for sensitivity assessments of key efficacy analyses.

#### **4.1.2 Subject Disposition**

The number of subjects in the Safety population will be presented with the study completion status and the reasons for discontinuation.

#### **4.1.3 Demographic and Baseline Characteristics**

Demographic and baseline characteristics will be presented in the data listings. Descriptive summary statistics (n, mean, standard deviation, median, minimum, and maximum) and/or frequency distributions, as appropriate, will be generated for the Safety population.

#### **4.1.4 Diagnosis and Prior Therapies and Treatments for Atopic Dermatitis**

Prior therapies and treatment for atopic dermatitis will be summarized by frequency distributions. The time since diagnosis of atopic dermatitis will be summarized using descriptive statistics (n, mean, standard deviation, median, minimum, and maximum). Summaries will be generated for the Safety Population.

#### **4.1.5 History of Allergies**

Allergy history will be listed.

#### **4.1.6 Prior and Concomitant Medications, Therapies and Procedures**

Medications will be coded using the WHO Drug Reference (B3 Format Sept 2018). Prior and concomitant medications will be listed only. The period(s) in which the medications were administered will be flagged.

#### **4.1.7 Exposure to Study Medication and Study Medication Administration**

Exposure will be summarized and listed for the Safety population. The duration of treatment, total weight, total volume, and average volume per application will be summarized using descriptive statistics (n, mean, SD, median, minimum and maximum).

#### **4.1.8 Major Protocol Violations**

Protocol violations will be identified to measure adherence to key aspects the protocol. Prior to analysis, the sponsor will assess the data and identify all protocol violations. Specific data fields that will be examined to identify protocol violations include entrance inclusion/exclusion criteria and prohibited prior and concomitant medications as well as all violations identified by the investigator. All protocol violations will be listed.

### **4.2 Efficacy Endpoints**

The baseline for all efficacy measures will be the last non-missing value collected on or before the date of the first application of study medication. Analyses of post-baseline data will be performed on observed (non-missing) data based on nominal visits as collected on the CRF.

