5.1. Overview of Atopic Dermatitis

Atopic dermatitis or eczema is an inflammatory skin disorder characterized by dry, cracked, pruritic skin lesions that most often develops in childhood. Sixty percent of the reported cases develop within the first year of life and 85% of the cases develop by the age of 5 ([Weston, 2017](#)). The disorder often follows a pattern of spontaneous remission with intermittent flares of the disease and often continues into adulthood. The symptoms can range from mild to severe and can interfere with daily activities. While the disease is not a life-threatening illness, atopic dermatitis can significantly impact a patient's quality of life. In patients with moderate to severe disease the symptoms rarely clear without treatment. There are a number of topical treatment options including corticosteroids, calcineurin inhibitors, antihistamines, and antimicrobial agents that are used to treat atopic dermatitis however it has been over 15 years since a new topical therapy with a new mechanism of action has been approved.

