9.3. Subject Withdrawal Criteria

Subjects will be informed that they are free to withdraw from the study at any time and for any reason. The investigator may remove a subject from the study if, in the investigator's opinion, it is not in the best interest of the subject to continue the study. Examples of other reasons subjects may be discontinued from the study are: a change in compliance with an inclusion or exclusion criteria, occurrence of AEs, occurrence of pregnancy, use of a prohibited therapy or subject is unwilling or refuses to continue with the protocol defined procedures, treatments and/or study visits and/or subject withdraws consent.

The date the subject is withdrawn from the study and the reason for discontinuation must be recorded in the subject's electronic case report forms (eCRFs). All withdrawn subjects will be required to complete one last safety follow up visit approximately 30 days after last study medication application. If the subject withdraws their consent to have this visit completed this needs to be appropriately documented in the subject's source notes and on the subject's eCRF.

Subjects will be permanently discontinued from the study in the event of any of the following:

- Severe infection requiring parenteral antimicrobial therapy or hospitalization
- Symptomatic herpes zoster

- Malignancy – except for non-melanoma skin cancer (SCC or BCC) not in or near the treatment area
- Anaphylactic or severe allergic reaction
- WBC Count: $< 1 \times 10^9/L$ or second occurrence of $< 2 \times 10^9/L$
- ANC: $< 0.5 \times 10^9/L$ or second occurrence of $< 1 \times 10^9/L$
- Lymphocyte count: $< 0.3 \times 10^9/L$ or second occurrence of $< 0.5 \times 10^9/L$
- Platelet count: $< 50 \times 10^9/L$ or second event of $< 75 \times 10^9/L$ - in each case, value should be confirmed by retesting before treatment discontinuation
- Hemoglobin: $< 6.5 \text{ g/dL}$ or second occurrence of $< 8 \text{ g/dL}$ - in each case, value should be confirmed by retesting before treatment discontinuation
- AST or ALT:
 - $> 5 \times \text{ULN}$ persisting for 2-weeks of study medication interruption or second event of $> 5 \times \text{ULN}$
 - $3 \times \text{ULN}$ with total bilirubin $> 2 \times \text{ULN}$ or symptoms of hepatocellular injury [fatigue, nausea, vomiting, right upper quadrant pain or tenderness, fever, rash and/ or eosinophilia ($> 5\%$)].

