11.6. Prohibited Medications

While subjects are participating in this study they are prohibited from using the following medication/therapies:

- Phototherapy -Subjects must refrain from excessive sunlight (natural or artificial) and must apply sunscreen to all treatment areas if excessive exposure cannot be avoided.
- Systemic immunosuppressant or immunomodulatory therapy (e.g. etanercept, alefacept, infliximab, methotrexate)
- JAK inhibitors (systemic or topical)
- Systemic corticosteroids (intranasal and inhaled corticosteroids are allowed)
- Cytostatic agents
- Crisaborole
- Dupilumab or other monoclonal antibody for the treatment of AD
- Systemic antibiotics
- Topical treatments for atopic dermatitis (corticosteroids, calcineurin inhibitors, topical H1 and H2 antihistamines, topical antimicrobials, and other medicated topical agents)
- Prescription moisturizers
- Topical antibacterial medications or products, including soaps, bleach baths, or topical sodium hypochlorite-based products.
- Vaccine treatments

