14. STATISTICS

14.1. Statistical Methods

Safety and efficacy results will be summarized and presented by visit, with no inferential statistics presented. Parameters related to safety and tolerability will be treated as primary analysis variables. Efficacy parameters will be treated as secondary endpoints.

All data will be summarized by visit, with presentations based on the nature of the parameter. For binary data such as presence or absence of treatment-emergent adverse events, the incidence will be presented along with the overall number of subjects and percentages. External clinical laboratory and similar externally sourced data will be summarized as binary outcomes based on the determination of values beyond applicable normal ranges, and in some cases the assessment of clinical significance of deviations from normal ranges. For ordinal categorical data including efficacy data from PGA, EASI, SPA and SAD scores, and continuous data such as affected body surface area, summary statistics will be presented including N, mean, median, standard deviation, and standard error, by visit. Where applicable, the mean changes from baseline for ordinal categorical and continuous parameters will be presented by visit, along with N, median, standard deviation and standard error.

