### **4.4 Sample Size**

Sample size for this study was not based upon formal statistical criteria. A total of 30 subjects is planned.

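### SAP 4.2 lets scores taken after a prohibited AD therapy count as response to ATI-502, mainly at Week 8 and in the any-visit EASI-75 summary

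*SAP*

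**What the plan says.** SAP 4.2 sets one data rule for all efficacy measures: "Analyses of post-baseline data will be performed on observed (non-missing) data based on nominal visits as collected on the CRF". SAP 4.1.1 puts everyone with one application in the Efficacy Population. Its Per-Protocol Population, used for sensitivity, requires only that Visit 6 was completed.

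Protocol 11.6 opens with "While subjects are participating in this study they are prohibited from using the following medication/therapies" and then names, among others, topical and systemic corticosteroids, calcineurin inhibitors, crisaborole, dupilumab and phototherapy. Participation runs to Visit 6, although Protocol 7.4 gives study drug for 4 weeks only.

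Protocol 9.3 lists use of a prohibited therapy after the words "Examples of other reasons subjects may be discontinued from the study are". It is absent from that section's separate list of events that require permanent discontinuation.

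SAP 4.1.8 has the sponsor identify prohibited medication before analysis, but the only stated result is "All protocol violations will be listed". SAP 4.1.6 likewise only lists concomitant medications, with the period flagged. SAP 4.2.1 tabulates EASI-75 by visit and also as a response reached at any visit after baseline.

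**The concern.** The protocol itself makes the event foreseeable. Section 5.1 says of the disease: "The disorder often follows a pattern of spontaneous remission with intermittent flares of the disease and often continues into adulthood". It adds: "In patients with moderate to severe disease the symptoms rarely clear without treatment". Subjects entering with PGA 3 or 4 then spend about 4 weeks without study drug and without the listed alternatives before they are scored again.

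Once a subject has used another effective treatment, the score no longer measures ATI-502 alone. Those doing badly are the likeliest to reach for such treatment, so the probable direction of error favours the drug, and relapse after stopping could be hidden. There is no control arm to offset this. The any-visit EASI-75 summary carries the problem beyond the follow-up visit, because one improved Week 8 score can make a subject a responder overall.

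**Working it through.** **Figure in the plan.** There is nothing to reproduce. SAP 4.4 says: "Sample size for this study was not based upon formal statistical criteria. A total of 30 subjects is planned". No alpha, power, effect size or SD is given. What can be checked is how the rules act on one subject and what each such subject is worth.

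**Off-drug window.** The schedule of assessments ends treatment at Day 28 and puts Visit 6 at Day 56 with a window of +7 days. The window is 56 − 28 = 28 days, up to 63 − 28 = 35 days. EASI, PGA, BSA, SPA and SAD are all scheduled at Visit 6.

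**One subject traced through the rules.** A subject flares after Week 4, uses a topical corticosteroid on a target area, improves and attends Visit 6.

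- Withdrawal (Protocol 9.3): possible, not required. A withdrawn subject is still asked to return for a last safety visit, and the SAP does not say that scores from that visit are dropped.
- Efficacy Population: included.
- Per-Protocol Population: included if Visit 6 is completed, so the sensitivity analysis does not remove the problem.
- SAP 4.2: the score is non-missing, so it is used.
- SAP 4.2.1 to 4.2.3: if it crosses the threshold, it is a response at Week 8 and, for EASI-75, a response in the any-visit summary.

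**Which scales can be reached.** Under Protocol 12, PGA, BSA, SAD and SPA score target areas; under 11.1 these exclude scalp, face, palms, soles, groin and genitalia. EASI (12.3) covers the whole body. A topical used only on the face can therefore change EASI but not the other four.

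**Value of one subject.** With 30 scored, 1/30 = 3.3 percentage points.

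**Effect of the handling rule (assumed inputs).** Let 9 of 30 respond without other therapy, and let m further subjects reach the threshold only because of it. The rates are (9 + m)/30 as planned, 9/30 if the m count as non-responders, and 9/(30 − m) if their scores are set to missing.

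| m | As planned | Non-response | Set to missing |
|---|---|---|---|
| 1 | 33.3% | 30.0% | 31.0% |
| 3 | 40.0% | 30.0% | 33.3% |
| 6 | 50.0% | 30.0% | 37.5% |

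Setting scores to missing still overstates the rate, because subjects who would not have responded leave the denominator.

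**Chance that it happens at all (assumed use rate q).** P(at least one user) = 1 − (1 − q)^30.

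| q | Expected users (30q) | P(at least one) |
|---|---|---|
| 5% | 1.5 | 78.5% |
| 10% | 3 | 95.8% |
| 20% | 6 | 99.9% |

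If every user then met the criterion and none would have done so otherwise, the mean overstatement would equal q, that is 5, 10 or 20 points. That is an upper bound. The documents give neither q nor the share who would cross a threshold.

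**The case against.** The strongest reply concerns scope. The secondary outcomes are changes after 4 weeks of treatment, and Week 8 is labelled a safety follow-up. At Week 4 the problem needs a subject on open-label active drug to break 11.6 within 28 days. A reader might infer that the Week 4 outcomes are compromised; the documents do not show that. What stands is the exposure of the Week 8 tables and the any-visit EASI-75 summary, both of which the SAP plans to report.

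A reader might also infer that subjects go without any AD therapy until Week 8. They do not: they apply ATI-502 for 4 weeks, a stable oral H1 antihistamine is allowed at entry, and emollients may be used off the target areas.

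The direction of error is likely rather than certain. Someone already at EASI-75 who treats a small new flare adds nothing to the rate, and Section 5.1 also speaks of spontaneous remission. Analysing all observed values whatever else was taken is a recognised strategy too. But the SAP does not present its rule as that choice, and in a single-arm trial the resulting rate will be read as the effect of ATI-502.

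Partial safeguards exist. Discontinuation is possible, prohibited use is identified before analysis, and with about 30 subjects a reader could match listings to scores. None of these changes the tabulated rate. SAP 4.3 refers to a separate data-handling document, which was not available; it is mentioned only under safety.

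**Conclusion.** The gap is real and limited. Followed exactly, SAP 4.2 credits to ATI-502 any improvement caused by a prohibited AD therapy, and neither analysis population separates it. The tables at risk are the Week 8 responder tables and the any-visit EASI-75 summary; earlier visits are at risk only if such therapy starts during treatment.

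The one firm size is 3.3 points per subject who meets a criterion solely because of other therapy, with 30 scored. Any total rests on assumed use and response rates, so no particular overstatement can be claimed.

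No test or error rate is touched: efficacy is secondary, and Protocol 14.1 says "Safety and efficacy results will be summarized and presented by visit, with no inferential statistics presented". The harm is to how the response rates are read. This is a cheap improvement, not a defect that undermines the trial.

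**What to change.** Add to SAP 4.2, before anyone sees which subjects are affected:

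- **Responder tables (EASI-75, EASI-50, PGA, SAD).** From the start date of a prohibited AD therapy that can affect the scored skin, the subject counts as a non-responder at that and later visits. For EASI this means a systemic therapy or use at any body site; for PGA and SAD, a systemic therapy or use on a target area. In the any-visit EASI summary, scores after that date cannot create a response; one reached earlier still counts.
- **Sensitivity.** Show the all-observed version beside it. If the other therapy can only help, the two versions bracket the rate that would have been seen without it.
- **Mean and percent change (EASI, SPA, BSA).** Keep the all-observed table as planned and add a sensitivity table without the later values. State that this exclusion removes subjects who flared and can itself favour the drug.
- **Count.** Report the number of such subjects by visit.
- **Definition.** Name the 11.6 entries that count as AD therapy, since the list also holds items such as vaccines.

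The cost is a few lines of SAP text and a derived flag. Protocol 11.5 already requires new or modified therapies to be recorded, SAP 4.1.6 flags the period, and SAP 4.1.8 already screens for prohibited use. The documents do not say whether the application site of a topical is captured; if it is not, the PGA and SAD rule needs a site query or a stated default. The downside is that reported response rates may fall, by an amount that depends on how many subjects used such therapy; a subject who would have responded anyway is also counted as a non-responder. The prohibition itself is left as it is.
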